3.3 SELECTION OF TRIAL POPULATION

It is planned that 14 healthy male subjects will enter the study. They will be recruited from the volunteers' pool of the trial site. Because of the reproduction toxicity itraconazole has shown in nonclinical studies, only male subjects will be included in this study.

Proprietary confidential information © 2019 Boehringer Ingelheim International GmbH or one or more of its affiliated companies

A log of all subjects enrolled into the trial (i.e. who have signed informed consent) will be maintained in the Investigator Site File (ISF) irrespective of whether they have been treated with investigational drug or not.

3.3.1 Main diagnosis for trial entry

The study will be performed in healthy subjects.

3.3.2 Inclusion criteria

Subjects will only be included in the trial if they meet the following criteria:

1. Healthy male subjects according to the assessment of the investigator, as based on a complete medical history including a physical examination, vital signs (BP, PR), 12-lead ECG, and clinical laboratory tests
2. Age of 18 to 50 years (inclusive)
3. BMI of 18.5 to 29.9 kg/m² (inclusive)
4. Signed and dated written informed consent prior to admission to the study, in accordance with GCP and local legislation

3.3.3 Exclusion criteria

Subjects will not be allowed to participate, if any of the following general criteria apply:

1. Any finding in the medical examination (including BP, PR or ECG) deviating from normal and assessed as clinically relevant by the investigator
2. Repeated measurement of systolic blood pressure outside the range of 90 to 140 mmHg, diastolic blood pressure outside the range of 50 to 90 mmHg, or pulse rate outside the range of 45 to 90 bpm
3. Any laboratory value outside the reference range that the investigator considers to be of clinical relevance
4. Any evidence of a concomitant disease assessed as clinically relevant by the investigator
5. Gastrointestinal, hepatic, renal, respiratory, cardiovascular, metabolic, immunological or hormonal disorders
6. Cholecystectomy or other surgery of the gastrointestinal tract that could interfere with the pharmacokinetics of the trial medication (except appendectomy or simple hernia repair)
7. Diseases of the central nervous system (including but not limited to any kind of seizures or stroke), and other relevant neurological or psychiatric disorders
8. History of relevant orthostatic hypotension, fainting spells, or blackouts
9. Chronic or relevant acute infections
10. History of relevant allergy or hypersensitivity (including allergy to the trial medication or its excipients)

Proprietary confidential information © 2019 Boehringer Ingelheim International GmbH or one or more of its affiliated companies

11. Use of drugs within 30 days of planned administration of trial medication that might reasonably influence the results of the trial (including drugs that cause QT/QTc interval prolongation)
12. Intake of an investigational drug in another clinical trial within 60 days of planned administration of investigational drug in the current trial, or concurrent participation in another clinical trial in which investigational drug is administered
13. Smoker (more than 10 cigarettes or 3 cigars or 3 pipes per day)
14. Inability to refrain from smoking on specified trial days
15. Alcohol abuse (consumption of more than 30 g per day)
16. Drug abuse or positive drug screening
17. Blood donation of more than 100 mL within 30 days of planned administration of trial medication or intended blood donation during the trial
18. Intention to perform excessive physical activities within one week prior to the administration of trial medication or during the trial
19. Inability to comply with the dietary regimen of the trial site
20. A marked baseline prolongation of QT/QTc interval (such as QTc intervals that are repeatedly greater than 450 ms) or any other relevant ECG finding at screening
21. A history of additional risk factors for *Torsade de Pointes* (such as heart failure, hypokalaemia, or family history of Long QT Syndrome)
22. Subject is assessed as unsuitable for inclusion by the investigator, for instance, because the subject is not considered able to understand and comply with study requirements, or has a condition that would not allow safe participation in the study

In addition, the following trial-specific exclusion criteria apply:

23. Liver enzyme (ALT, AST, GGT) values above upper limit of normal at the screening examination
24. History of drug-induced liver injury
25. History of heart failure, or any evidence of ventricular dysfunction in the history
26. History of hereditary fructose intolerance
27. Male subjects with WOCBP partner who are unwilling to use male contraception (condom or sexual abstinence) from time point of first administration of trial medication until 30 days after the last administration of trial medication
28. Haemoglobin or Red Blood Cell Count below the lower limit of normal at the screening examination
29. White Blood Cell Count or Neutrophil Count outside the normal range at the screening examination

For study restrictions, refer to Section [4.2.2](#).

3.3.4 Withdrawal of subjects from treatment or assessments

Subjects may discontinue trial treatment or withdraw consent to trial participation as a whole ('withdrawal of consent') with very different implications; please see sections [3.3.4.1](#) and [3.3.4.2](#) below.

If a subject is removed from or withdraws from the trial prior to the first administration of trial medication, the data of this subject will not be entered in the case report form (CRF) and will not be reported in the clinical trial report (CTR). If a subject is removed from or withdraws from the trial after the first administration of trial medication, this will be documented and the reason for discontinuation must be recorded in the CRF; in addition, the data will be included in the CRF and will be reported in the CTR. At the time of discontinuation, a complete end of trial examination will be performed, if possible, and the information will be recorded in the CRF. If the discontinuation occurs before the end of the REP (see Section [1.2.3](#)), the discontinued subject should if possible be questioned for AEs and concomitant therapies at or after the end of the REP in order to ensure collection of AEs and concomitant therapies throughout the REP, if not contrary to any consent withdrawal of the subject.

3.3.4.1 Discontinuation of trial treatment

An individual subject will discontinue trial treatment if:

1. The subject wants to discontinue trial treatment, without the need to justify the decision
2. The subject has repeatedly shown to be non-compliant with important trial procedures and, in the opinion of both, the investigator and sponsor representative, is not willing or able to adhere to the trial requirements in the future.
3. The subject needs to take concomitant medication that interferes with the investigational medicinal product or other trial treatment
4. The subject can no longer receive trial treatment for medical reasons (such as surgery, adverse events [AEs], or diseases)
5. The subject has an elevation of AST and/or ALT ≥ 3 -fold ULN and an elevation of total bilirubin ≥ 2 -fold ULN (measured in the same blood sample) and/or needs to be followed up according to the DILI checklist provided in the ISF

In addition to these criteria, the investigator may discontinue subjects at any time based on his or her clinical judgment.

Even if the trial treatment is discontinued, the subject remains in the trial and, given his/her agreement, will undergo the procedures for early treatment discontinuation and follow up as outlined in the [Flow Chart](#) and section [6.2.3](#).

3.3.4.2 Withdrawal of consent to trial participation

Subjects may withdraw their consent to trial participation at any time without the need to justify the decision. If a subject wants to withdraw consent, the investigator should be involved in the discussion with the subject and explain the difference between trial treatment

Proprietary confidential information © 2019 Boehringer Ingelheim International GmbH or one or more of its affiliated companies

discontinuation and withdrawal of consent to trial participation, as well as explain the options for continued follow up after trial treatment discontinuation, please see section [3.3.4.1](#) above

3.3.4.3 Discontinuation of the trial by the sponsor

Boehringer Ingelheim reserves the right to discontinue the trial at any time for any of the following reasons:

1. Failure to meet expected enrolment goals overall or at a particular trial site
2. New toxicological findings, serious adverse events, or any safety information invalidating the earlier positive benefit-risk-assessment. More specifically, the trial will be terminated if more than 50% of the subjects have drug-related and clinically relevant adverse events of moderate or severe intensity, or if at least 1 drug-related serious adverse event is reported
3. Violation of GCP or the CTP impairing the appropriate conduct of the trial
4. The sponsor decides to discontinue the further development of the investigational product

3.3.5 Replacement of subjects

In case more than 2 subjects do not complete the trial, the Clinical Trial Leader together with the Trial Pharmacokineticist and the Trial Statistician are to decide, if and how many subjects will be replaced. A replacement subject will be assigned a unique trial subject number, and will be assigned to the same treatment as the subject █ replaces.

4. TREATMENTS

4.1 INVESTIGATIONAL TREATMENTS

The investigational product BI 730357 as tablet formulation has been manufactured by BI Pharma GmbH & Co. KG. Itraconazole oral solution will be obtained from a public pharmacy.

4.1.1 Identity of the Investigational Medicinal Products

The characteristics of the two test products are given below:

Test product 1

Substance:	BI 730357
Pharmaceutical formulation:	Tablet
Source:	BI Pharma GmbH & Co. KG, Germany
Unit strength:	50 mg
Posology:	1 – 0 – 0
Route of administration:	Oral
Duration of use:	1 day (in treatments R and T)

Test product 2

Name:	Sempera® Liquid 10 mg/ml
Substance:	Itraconazole
Pharmaceutical formulation:	Oral solution
Source:	Public pharmacy (obtained by the clinical site)
Holder of marketing authorization:	JANSSEN-CILAG GmbH, Neuss, Germany
Unit strength:	10 mg/mL
Posology:	20 mL – 0 – 0
Route of administration:	Oral
Duration of use:	12 days (in treatment T, only)

4.1.2 Selection of doses in the trial

Perpetrator (itraconazole)

The dose of itraconazole selected for this trial reflects standard clinical doses, is considered sufficient to yield significant CYP3A inhibition and has been used successfully and safely in previous drug-drug interaction trials ([c02336088](#), [c03355329](#), [c08928447](#)).

Victim (BI 730357)

Based on *in vitro* data, CYP3A is responsible for approximately 90% of the metabolism of BI 730357. If metabolic clearance is the main pathway of BI 730357 elimination, concomitant administration of BI 730357 with the strong CYP3A inhibitor itraconazole may result in substantial increases of BI 730357 plasma concentrations.

For the current trial, a dose of 50 mg BI 730357 is selected, in order to ensure that BI 730357 plasma concentrations, even in case of a substantial increase when given with itraconazole, are within the range of concentrations that were explored in the SRD part of trial 1407-0001 and that were associated with good safety and tolerability.

In the SRD part of trial 1407-0001, single oral doses of 2 to 800 mg BI 730357 were administered as oral solution or tablet formulation under fasting or fed conditions, and available data indicate that, at all doses tested, BI 730357 administration was safe and well tolerated.

I.e., the ratios of gMean plasma exposure parameters at 800 mg and at 50 mg were approximately 14 (C_{max}) and 13 (AUC_{0-24}). These ratios are assessed to be sufficient as safety margins for the current trial, to cover for increases of BI 730357 plasma exposures when given together with itraconazole (see also section [1.4.3.3](#)).

4.1.3 Method of assigning subjects to treatment groups

There is only one treatment sequence investigated in this trial, and each subject will be allocated to the same treatment sequence (R-T). The subjects will be allocated to a study subject number by drawing lots prior to first administration of trial medication in the morning of Day 1 of Visit 2. The randomization list of study subject numbers and assigned treatment sequence will be provided to the trial site in advance. Note that the randomization list is just needed for logistical reasons in this non-randomized, open-label trial. Hence, no bias is introduced when providing the randomization list in advance to the site. Reference and test treatments will be administered in the sequence specified in the [Flow Chart](#).

Once a subject number has been assigned, it cannot be reassigned to any other subject.

All subjects may be treated in one cohort, i.e. all subjects may receive treatment on the same calendar day. In case this is not feasible (e.g., due to logistical or recruitment reasons), the group may be split into several cohorts as required. Treatment of all subjects on the same calendar day is acceptable (for safety margin to exposure reached in previous SRD trial 1407.1 refer to Section 1.4.3.3; for discussion of study-associated risks and safety measures see Section [1.4.3](#)).

The randomisation procedure is described in Section [7.6](#).

4.1.4 Drug assignment and administration of doses for each subject

This trial is a one-way crossover study. All subjects will receive the 2 treatments in fixed order. The treatments to be evaluated are outlined in Table [4.1.4: 1](#) below.

Table 4.1.4: 1 Dosage and treatment schedule

Treatment period	Treatment	Substance	Formulation	Unit strength	Dosage	Total dose
1	R (Reference)	BI 730357	Tablet	50 mg	1 tablet on Day 1	50 mg
2	T (Test)	BI 730357 Itraconazole	Tablet Oral solution	50 mg 10 mg/mL	1 tablet on Day 1 20 mL (200 mg) on Days -3 to Day 9	50 mg 2400 mg

Administration of trial medication will be performed after subjects have fasted overnight; fasting is to start no later than 10 h before the scheduled dosing of BI 730357 and no later than 9 h before dosing of itraconazole.

The investigator (or authorised designee) will administer the trial medication as an oral dose together with about 240 mL of water to subjects who are in a standing position. For drug administration, the so-called four-eye principle (two-person rule) should be applied. For this, one authorised employee of the trial site should witness the administration of trial medication, and – if applicable – its preparation (e.g. reconstitution), if correct dosage cannot be ensured otherwise.

For restrictions with regard to diet, see Section [4.2.2.2](#).

Subjects will be kept under close medical surveillance until 24 h after drug administration of BI 730357. During the first 4 h after drug administration of BI 730357, subjects are not allowed to lie down (i.e. no declination of the upper body of more than 45 degrees from upright posture), except for medical reasons or for recording of 12-lead ECG and vital signs measurements.

The treatments will be separated by a wash-out phase of at least 10 days between administrations of BI 730357.

4.1.5 Blinding and procedures for unblinding

This Phase I trial will be handled in an open fashion throughout (that is, during the conduct, including data cleaning and preparation of the analysis). This is considered acceptable because the potential for bias seems to be low and does not outweigh practical considerations.

Emergency envelopes will not be provided, because the dose of trial medication is known to investigators and subjects.

4.1.6 Packaging, labelling, and re-supply

BI 730357 tablets

BI 730357 tablets will be provided by BI. They will be packaged and labelled in accordance with local law and the principles of Good Manufacturing Practice. For details of packing and the description of the label, refer to the ISF.

The telephone number of the sponsor and the name, address and telephone number of the trial site are provided in the subject information form. The EudraCT number is indicated on the title page of this protocol as well as on the subject information and informed consent forms.

No re-supply is planned.

Itraconazole oral solution

Itraconazole oral solution will be obtained by the clinical trial site from a public pharmacy. The drug will be dispensed out of the original, unmodified packages.

4.1.7 Storage conditions

Drug supplies will be kept in their original packaging and in a secure limited access storage area in accordance with the recommended (labelled) storage conditions. If necessary, a temperature log must be maintained to make certain that the drug supplies are stored at the correct temperature. If the storage conditions are found to be outside the specified range, the Clinical Trial Manager (as provided in the list of contacts) is to be contacted immediately.

4.1.8 Drug accountability

The investigator or designee will receive the investigational drugs delivered from the sponsor following requirements are fulfilled:

- Approval of the clinical trial protocol by the IRB / ethics committee
- Approval/notification of the regulatory authority, e.g. competent authority
- Availability of the *curriculum vitae* of the Principal Investigator
- Availability of a signed and dated clinical trial protocol

Only authorised personnel documented in the form 'Trial Staff List' may dispense medication to trial subjects. The trial medication must be administered in the manner specified in the CTP.

The investigator or designee must maintain records of the product's delivery to the trial site, the inventory at the site, the use by each subject, and the disposal of unused products. These records will include dates, quantities, batch / serial numbers, expiry ('use-by') dates, and the unique code numbers assigned to the investigational medicinal product and trial subjects. The investigator or designee will maintain records that document adequately that the subjects were provided the doses specified by the CTP and reconcile all investigational medicinal products received from the sponsor. At the time of disposal of remaining trial medication, the investigator or designee must verify that no remaining supplies are in the investigator's possession.

All unused medication will be disposed of locally by the trial site upon written authorisation of the Clinical Trial Leader. Receipt, usage and disposal of trial medication must be documented on the appropriate forms. Account must be given for any discrepancies.

4.2 OTHER TREATMENTS, EMERGENCY PROCEDURES, RESTRICTIONS

4.2.1 Other treatments and emergency procedures

There are no special emergency procedures to be followed. No additional treatment is planned. However, if adverse events require treatment, the investigator can authorise symptomatic therapy. In those cases, subjects will be treated as necessary and, if required, kept under supervision at the trial site or transferred to a hospital until all results of medical evaluations are acceptable.

4.2.2 Restrictions

4.2.2.1 Restrictions regarding concomitant treatment

In principle, no concomitant therapy is allowed. All concomitant or rescue therapies will be recorded (including time of intake on study days) on the appropriate pages of the CRF.

Known inhibitors/inducers of CYP3A as well as drugs with a known hepatotoxicity profile should be avoided during the entire study.

4.2.2.2 Restrictions on diet and life style

Poppy-seeds containing foods should not be consumed starting 3 days before the first drug administration in each treatment period, in order to avoid false-positive results in the drug screen.

While admitted to the trial site, the subjects will be instructed not to consume any foods or drinks other than those provided by the staff. Standardised meals will be served at the times indicated in the [Flow Chart](#).

No food is allowed within 10 h before and 4 h after intake of BI 730357.

Subjects will be advised to not consume any food within 9 h before and 1 h after itraconazole administration.

From 1 h before intake of BI 730357 on Day 1 of Period 1 until lunch, and from 1 h before intake of itraconazole on Day 1 of period 2 until lunch, fluid intake is restricted to the water administered with the drug, and an additional 240 mL of water at 2 h and 4 h post-dose (mandatory for all subjects). From lunch until 24 h post-dose, total fluid intake is restricted to 3000 mL.

Grapefruits, Seville oranges (sour or bitter oranges) and their juices, and dietary supplements and products containing St. John's wort (*Hypericum perforatum*) are not permitted from 7 days before the first administration of trial medication in Period 1 until after the last PK sample of Period 2 is collected.

Alcoholic beverages are not permitted from 2 days before the first administration of trial medication in period 1 until after the last PK sample in period 2 is collected.

Methylxanthine-containing drinks or foods (such as coffee, tea, cola, energy drinks, or chocolate) are not allowed from 10 h before until 24 h after administration of BI 730357.

Proprietary confidential information © 2019 Boehringer Ingelheim International GmbH or one or more of its affiliated companies

Smoking is not allowed during in-house confinement while admitted to the trial site.

Excessive physical activity (such as competitive sport) should be avoided from 7 days before the first administration of trial medication until the end of trial examination.

Direct exposure to the sun or exposure to solarium radiation, treatment with ultraviolet light (e.g. PUVA), or medication with known phototoxicity potential (e.g. doxycycline) should be avoided from the first administration of trial medication until the EoTrial examination. The use of sunscreens is mandatory in that time.

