			5:00	14:00		x				
			6:00	15:00		x				
			7:00	16:00	Snack (voluntary)		x			
			8:00	17:00						
			10:00	19:00	Dinner	x				
			12:00	21:00		x				
			2	24:00	09:00	Breakfast (voluntary) ¹⁰ , discharge from trial site	B	x		
			34:00	19:00	Ambulatory visit	x				
			3	47:00	08:00	Ambulatory visit	x			
			4	71:00	08:00	Ambulatory visit	x			
			6	119:00	08:00	Ambulatory visit	B	x		
			8	167:00	08:00	Ambulatory visit	x	x		

Proprietary confidential information © 2019 Boehringer Ingelheim International GmbH or one or more of its affiliated companies

FLOW CHART (cont'd)

Period	Visit	Day	Planned time (relative to BI 73 0357 administration) [h:min]	Approximate clock time of actual day [h:min]	Event and comment	Safety laboratory ⁹	PK _{blood} (BI 730357 +	12-lead ECG	Vital signs (BP, PR)	Questioning for AEs and concomitant therapy ⁶
Period 2 / Treatment T (BI 730357 + itraconazole) ⁷	3	-3	-73:00	08:00	Ambulatory visit, itraconazole administration	B ^{2,5}			x ²	
		-2	-49:00	08:00	Ambulatory visit, itraconazole administration				x ²	
		-1	-25:00	08:00	Ambulatory visit, itraconazole administration				x ²	
		1	-3:00	06:00	Admission to trial site		x ²		x ²	x ²
			-1:00	08:00	Itraconazole administration					
			0:00	09:00	BI 730357 administration					
			0:30	09:30			x			
			1:00	10:00			x			
			1:30	10:30			x		x	x
			2:00	11:00	240 mL fluid intake		x			
			2:30	11:30			x			
			3:00	12:00			x			
			3:30	12:30			x			
			4:00	13:00	240 mL fluid intake, thereafter lunch ¹⁰		x		x	x
			5:00	14:00			x			
			6:00	15:00			x			
			7:00	16:00	Snack (voluntary)					
			8:00	17:00			x			
			10:00	19:00	Dinner					
			12:00	21:00			x			x
		2	23:00	08:00	Itraconazole administration					x
			24:00	09:00	Breakfast (voluntary) ¹⁰ , discharge from trial site	B ²	x	x	x	x
			34:00	19:00	Ambulatory visit		x			x
			3	47:00	08:00	Ambulatory visit, itraconazole administration	x ¹¹			x ²
			4	71:00	08:00	Ambulatory visit, itraconazole administration	C ²	x ¹¹		x ²
			5	95:00	08:00	Ambulatory visit, itraconazole administration				x ²
			6	119:00	08:00	Ambulatory visit, itraconazole administration	B ²	x ¹¹		x ²
			7	143:00	08:00	Ambulatory visit, itraconazole administration				x ²
			8	167:00	08:00	Ambulatory visit, itraconazole administration	C ²	x ¹¹		x ²
			9	191:00	08:00	Ambulatory visit, itraconazole administration				x ²
			10	215:00	08:00	Ambulatory visit		x		x
			12	263:00	08:00	Ambulatory visit		x		x
FU	4	18 to 25			End of trial (EoTrial) examination ⁴	D		x	x	x

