1. Subject must be informed and written informed consent obtained prior to starting any screening procedures. Screening procedures include physical examination, check of vital signs, ECG, safety laboratory (including drug screening), demographics (including determination of body height and weight, smoking status and alcohol history), relevant medical history, concomitant therapy and review of inclusion/exclusion criteria. Pharmacogenetic samples will be collected if needed.
2. The time is approximate; the procedure is to be performed and completed within 2h prior to itraconazole administration.
3. The time is approximate; the procedure is to be performed and completed within 3h prior to BI 730357 administration.
4. At the end of trial visit the EoTrial examination includes physical examination, vital signs, ECG, safety laboratory, recording of AEs and concomitant therapies.

Proprietary confidential information © 2019 Boehringer Ingelheim International GmbH or one or more of its affiliated companies

5. Period 1: Urine drug screening and alcohol breath test only; Period 2: Including urine drug screening and alcohol breath test.
6. AEs and concomitant therapies will be recorded throughout the trial, but will be specifically asked for at the times indicated in the [Flow Chart](#) above.
7. Treatments R and T will be separated by a wash-out period of at least 10 days between administrations of BI 730357
8. Safety laboratory to be taken and to be medically evaluated within 75 hours prior to first dosing of BI 730357; this safety laboratory assessment can be omitted if the screening examination is performed on Days -3, -2 or -1
9. Letter A, B, C and D define different sets of safety laboratory examinations (see Section [5.2.3](#))
10. If several actions are indicated at the same time, the intake of meals will be the last action.
11. Blood collection takes place exactly at the indicated times.

TABLE OF CONTENTS

TITLE PAGE	1
CLINICAL TRIAL PROTOCOL SYNOPSIS	2
FLOW CHART	4
TABLE OF CONTENTS	7
ABBREVIATIONS	11
1. INTRODUCTION	14
1.1 MEDICAL BACKGROUND	14
1.2 DRUG PROFILE	14
1.2.1 BI 730357	14
1.2.1.1 Nonclinical data	14
1.2.1.1.1 Efficacy and selectivity	14
1.2.1.1.2 Safety pharmacology	15
1.2.1.1.3 Toxicology	15
1.2.1.1.4 Non-clinical pharmacokinetics	17
1.2.1.2 Clinical data	17
1.2.1.2.1 Clinical pharmacokinetics and metabolism	18
1.2.1.2.2 Clinical safety	18
1.2.2 Itraconazole	19
1.2.3 Residual Effect Period	19
1.3 RATIONALE FOR PERFORMING THE TRIAL	20

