1.2.3 Residual Effect Period

The Residual Effect Period (REP, i.e., the period after the last dose with measurable drug levels and/or pharmacodynamic effects still likely to be present) of BI 730357 is 7 days for the mono-therapy (Treatment R). When given together with itraconazole (Treatment T), it is expected that plasma exposure of BI 730357 could be increased (albeit within the range explored in the clinical trial 1407-0001), and the time of relevant plasma exposure could be prolonged, which in turn could result in a prolonged period in which adverse effects could potentially occur.

For the use of itraconazole in Treatment T, the REP is defined as 9 days after last administration of itraconazole on Day 9 in Period 2. Therefore, the follow-up period will start earliest on Day 18 following BI 730357 dosing in Period 2, as this is expected to cover the period in which any potential adverse effects could reasonably occur.

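### The alcohol restriction ends on Day 12 of Period 2, 6 to 13 days before the only scheduled liver test after the last two itraconazole doses, so a late liver finding can be confounded by alcohol

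*Protocol*

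**What the plan says.** **Restrictions.** Protocol 4.2.2.2 states: "Alcoholic beverages are not permitted from 2 days before the first administration of trial medication in period 1 until after the last PK sample"; the sentence goes on to specify Period 2. The grapefruit and St John's wort restriction has the same end point. Two others in that section last longer: excessive physical activity "should be avoided from 7 days before the first administration of trial medication until the end of trial examination", and the sun-exposure limits, which run to the same examination. In 4.2.2.1, "drugs with a known hepatotoxicity profile should be avoided during the entire study".

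**Liver tests.** The Period 2 Flow Chart marks safety laboratories on Days -3, 2, 4, 6 and 8, and none on Day 10 or Day 12. The next is set D at the "End of trial (EoTrial) examination", Day 18 to 25. Footnote 2, which applies to the Day 8 sample, says "the procedure is to be performed and completed within 2h prior to itraconazole administration". Table 5.2.3: 1 includes AST, ALT and GGT in every set.

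**Residual effect period.** Protocol 1.2.3 says "the REP is defined as 9 days after last administration of itraconazole on Day 9 in Period 2" and "the follow-up period will start earliest on Day 18 following BI 730357 dosing in Period 2".

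**The concern.** Hepatotoxicity is the itraconazole risk that Protocol 1.4.3.2 and 1.4.4 single out, and hepatic injury is an adverse event of special interest (5.2.6.1.4). The plan treats the time up to the end of trial as still exposed. Follow-up is set to cover it, and hepatotoxic drugs are kept out throughout. Alcohol is released partway through that time.

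If a subject's AST, ALT or GGT is raised at the end-of-trial visit, the investigator has to judge whether treatment T caused it. Recent alcohol is then a possible alternative explanation, and the plan does not provide for documenting it. Breath alcohol tests are scheduled only on Day 1 of Period 1 and Day -3 of Period 2 (5.2.3). Alcohol history is a screening item. The scheduled questioning covers adverse events and concomitant therapy. What is at stake is the causality call on a late liver finding in an individual subject.

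**Working it through.** **Inputs**
- BI 730357 dose in Period 2: Day 1, 09:00, time 0 (Flow Chart).
- Itraconazole: Days -3 to -1 and Days 1 to 9, last dose at 191 h (Flow Chart, Table 4.1.4: 1).
- Day 8 laboratory: 167 h, before that day's dose (Flow Chart, footnote 2).
- Last PK sample and end of the alcohol restriction: 263 h (Flow Chart, 4.2.2.2).
- Residual effect period: 9 days after the last itraconazole dose (1.2.3).
- End-of-trial laboratory: Day 18 to 25 (Flow Chart).

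**Reproducing the plan's own figures**
- Itraconazole doses: 3 + 9 = 12, and 12 × 200 mg = 2400 mg, as in Table 4.1.4: 1.
- End of the residual effect period: 191 h + 9 × 24 h = 407 h, which is Day 18 at 08:00. This matches the stated earliest start of follow-up.

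**Placing the alcohol restriction on that calendar**
- 263 h is Day 12 at 08:00.
- Residual effect period without the restriction: (407 − 263)/24 = 6 days, or 6/9 = 67% of it.
- Days with alcohol permitted before the end-of-trial laboratory: 18 − 12 = 6 to 25 − 12 = 13.

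**Placing the liver tests**
- Gap between the Day 8 and end-of-trial laboratories: 18 − 8 = 10 to 25 − 8 = 17 days.
- Doses before the Day 8 sample: 3 (Days -3 to -1) + 7 (Days 1 to 7) = 10 of 12. The Day 8 and Day 9 doses follow it, and the end-of-trial test is the only scheduled liver test after them.

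**Where a late finding would be counted**
- SAP 6.1 ends the BI + ITZ phase 9 days after the last itraconazole dose, so on Day 18. The end-of-trial visit is on Day 18 to 25. A laboratory finding first dated to that visit therefore falls mostly in the follow-up phase FU-BI+ITZ.
- The Section 15.3 displays of the trial report leave out follow-up, so such a finding would mostly appear only in the displays that show follow-up separately.
- An event with onset between Day 12 and Day 18, for example symptoms that lead to an unscheduled test, would still be counted under BI + ITZ.

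**The case against.** The strongest reply is that nothing here contradicts itself. The alcohol restriction stops together with the grapefruit and St John's wort restriction, which fits a purpose of protecting the PK samples, and it covers every one of them. Restrictions with different purposes may end at different times, and the protocol nowhere promises abstinence to the end of trial. That stands: this is a gap in the design, not a contradiction.

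Existing provisions also reduce the problem:
- Five Period 2 samples (Days -3, 2, 4, 6 and 8) are taken under the restriction, and the Day 8 one follows 10 of the 12 itraconazole doses. Each subject has his own alcohol-free enzyme profile. In Table 5.2.3: 1 as it can be read, set C (Days 4 and 8) has no bilirubin, so for bilirubin the last such sample is Day 6.
- Causality assessment must weigh confounders and alternative explanations (5.2.6.1.6), and clinically relevant abnormal values are followed up (6.2.3).
- Symptoms of hepatic injury call for liver values, if necessary from an unscheduled test (5.2.6.1.4).
- Intake above 30 g per day and raised liver enzymes at screening are exclusions (3.3.3), and breath tests may be repeated at discretion (5.2.3).

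These provisions limit the harm but do not remove the gap. Weighing a confounder requires knowing about it, and no alcohol check or record is scheduled after Day 12. The case for keeping the present end point would be stronger if the protocol explained why hepatotoxic drugs stay restricted to the end while alcohol does not.

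**Conclusion.** The point holds as a minor one. Alcohol is permitted for 6 of the 9 days of the residual effect period, and for 6 to 13 days before the only scheduled liver test after the last two itraconazole doses. A late AST, ALT or GGT rise can be confounded by it; it need not be, because alcohol is permitted and not given. The effect is confined to case-level causality and special-interest assessment. PK endpoints are unaffected.

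Three stronger readings are not supported:
- *A late rise could not be told apart from an alcohol effect.* The five earlier samples, the follow-up of abnormal values and the duty to weigh confounders all help to separate them.
- *The drug-related adverse event tables become unreliable.* Under SAP 6.1 most such findings belong to FU-BI+ITZ, outside the main on-treatment displays.
- *The itraconazole still present when the restriction lifts measures the harm.* With the half-life of about 40 h in Protocol 1.2.2, 2^(−72/40) = 0.29 would remain after 72 h (263 − 191). That does not say how often alcohol raises enzymes, and the same section calls the kinetics non-linear.

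The verdict assumes that some subjects drink after Day 12 and that this can raise liver values. The documents give no rate for either. The number affected could be anywhere from 0 to 14 and is probably small.

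**What to change.** The sponsor should reconcile the end of the alcohol restriction in 4.2.2.2 with the residual effect period in 1.2.3 and the end-of-trial laboratory. One way is to use the end point that the section already applies to physical activity and sun exposure, the end-of-trial examination. This changes one phrase in the protocol and the matching line of the subject information. It costs 6 to 13 further days of abstinence for 14 healthy men, and no extra visit, sample or analysis.

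This does not add a liver sample between Day 8 and Day 18, nor a check that the restriction is kept. If the sponsor prefers the present end point, a sentence giving the reason and a recorded question on alcohol intake at the end-of-trial visit would at least document the confounder.
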